It is a potent neurotoxin that blocks neuromuscular transmission. Some authors have reported that botulinum toxin type A can minimize scar formation by reducing muscle tension during wound healing, causing the fibroblast cell cycle to be paused in a non-proliferative state and influencing TGF- β 1 expression (Lee and Janget., 2018).

1

Statement of the problem:

Does Botulinum toxin type A iontophoresis help in minimizing postburn hypertrophic scars?

Purpose of the study:

The main objective of the study is to evaluate the therapeutic effect of Botulinum toxin type A iontophoresis in improving postburn hypertrophic scars.

Significance of the study:

Hypertrophic scars result from fibroblast proliferation which is responsible for the enhanced collagen production that leads to excessive scarring. By decreasing the tension in the scar, botulinum toxin causes local fibroblasts to gradually change their functional status to proliferate slower, secrete less biologically active mediators and synthesize less extracellular matrix and collagen resulting in the improvement of hypertrophic scars (Elhefnawy., 2016).

One of the most significant drawbacks of BTX-A injection is pain. Iontophoresis, as an alternative modality for drug delivery, has several advantages. It is a painless modality with a reduction of systemic adverse effects due to localized drug administration and its convenience to the patient (Montaser-Kouhsari et al., 2014).

Delimitations:

This study was delimited in the following aspects:

1. Subjects:

Seventy-six patients with postburn hypertrophic scar will be randomly divided into two equal groups each one has 38 patients.

2. Equipment and tools:

2.1. Measurement equipment:

- Sonography (**Reinholz et al., 2016**).
- Patient and Observer Scar Assessment Scale (POSAS) (Reinholz et al., 2016).

2.2. Therapeutic equipment:

• Iontophoretic device.

Hypothesis:

It will be hypothesized that:

Botulinum toxin type A iontophoresis may help in minimizing postburn hypertrophic scars.

Basic Assumptions:

It will be assumed that:

- All patients will receive the same kinds of medication and the same nursing care.
- All subjects are free from any old previous hypertrophic scars.
- All subjects will continue in the study.
- All patients will follow the instructions during the treatment

Definitions of terms:

The following terms are defined for clear understanding of the terminology used in the present study:

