An iontophoretic device consists of four parts: power source, control circuit, electrodes, and reservoirs. The power source can be connected to the skin through a control circuit and two electrodes (the anode and the cathode). Two electrodes are attached to two reservoirs (one reservoir containing drug ions and the other containing physiologically compatible salts such as NaCl). Generally, Ag/AgCl is selected as the electrode material in iontophoretic systems (Wang et al., 2021).

3.4: Iontophoretic delivery of peptides and proteins:

Iontophoresis transiently increases the skin permeability of peptides and proteins. Peptides and proteins play a determining role in modern therapy. Their potency and specificity make them excellent therapeutic agents; however, their physicochemical properties and stability requirements almost invariably necessitate their administration by subcutaneous, intramuscular or intravenous injection. These act as effector agents that regulate and/or mediate physiological processes, serving as hormones, neurotransmitters and signal transducing factors. It has long been known that iontophoresis can administer therapeutic amounts of biologically active peptides into the body. More recent studies have shown that it is also capable of delivering structurally intact, functional proteins non-invasively into and across intact human skin and becomes the most popular choice of drug delivery (Dhote et al., 2012).

CHAPTER III

SUBJECTS, MATERIALS AND METHODS

In this part of the study, the materials and methods will be presented under the following headings: subjects, equipment, procedures of the study and statistical procedures.

1-Subjects (Sample size):

Sample size calculation is performed using G*POWER statistical software (version 3.1.9.2; Franz Faul, Universitat Kiel, Germany) based on data of VSS from the previous study (Elshahed et al., 2020) who reported a significant effect of botulinum toxin compared with control in treating hypertrophic scars. The required sample size for this study was 38 subjects per group. Calculations were made using α =0.05, power 90% and effect size = 0.76 and allocation ratio N2/N1 =1.

Seventy-six patients who have postburn hypertrophic scars will participate in this study. Their ages will be ranged from 20 to 40 years. The participants will be selected from the outpatient clinic of the faculty of physical therapy, at Cairo University and randomly distributed into two equal groups.

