1.1 Design of the study:

In this study, the patients will be randomly assigned into two equal groups (38 patients for each group).

1.1(a) Group A (Study group):

This group includes 38 postburn hypertrophic scar patients who will receive Botox iontophoresis once monthly for 3 months; in addition to their physical therapy program (Positioning, Stretching exercises,

11

Pressure Therapy and Massage) 2 sessions per week for 3 months (Mowafy et al., 2021).

1.1(b) Group B (Control group):

This group includes 38 patients who will receive traditional physical therapy (Positioning, Stretching exercises, Pressure Therapy and Massage) 2 sessions per week for 3 months (Mowafy et al., 2021).

1.2 Criteria for the patient selection:

1.2. a. Inclusion Criteria:

The subject selection will be according to the following criteria:

- Patient with hypertrophic scar (3-6) months after burn healing.
- Age range between 20-40 years.
- Male and female patients will participate in the study.
- All patients have a postburn hypertrophic scar at different body sites.
- All patients enrolled on the study will have their informed consent.

1.2.b Exclusion Criteria:

Exclusion Criteria related to iontophoresis (Sheikh and Dua., 2020):

- Patients with prior medical histories of cardiac arrhythmias.
- Patients with cardiac pacemakers.
- Patients with orthopaedic implants.
- Areas of skin with lesions and impaired sensation.
- During pregnancy and breastfeeding.
- Patient with diabetes mellitus.

Exclusion Criteria related to the delivered drug itself (Elshahed et al., 2020):

- Patients with a history of hypersensitivity or adverse reactions associated with (BTX A).
- Recent BTA administration 6 months before the study.
- Any subject complaining of psychiatric disorders or neurological disorders such as myasthenia gravis.

2-Equipment:

2.1-Measurement equipment:

2.1. (a)Sonography

A high-resolution B-image sonogram of every patient will be taken before and after treatment using an 11-Mhz receiving transducer of Logiq P6 Pro (GE Healthcare, Solingen, Germany). This method allows a good penetration depth of up to 40 mm into the skin and a resolution of around 158 micro m. It has been successfully utilized for objectively measuring pathological scars (**Reinholz et al., 2016**).

2.1. (b) Patient and Observer Scar Assessment Scale (POSAS)

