POSAS is an adequate tool to objectively measure scar quality and the therapeutic success of the applied scar treatment. It consists of two parts; one for the patient (Patient scale; POSAS Patient) and one for the physician (Observer scale; POSAS Observer). Both contain six items on a 10-point rating scale and an extra category "Overall Opinion". All characteristic features of the pathological scars are covered by the questionnaire: vascularity, pigmentation disorders, relief/texture, thickness, pliability, surface area, pain, and itching/pruritus. The latter items, in particular, concern the well-being of the patients (**Reinholz et al., 2016**).

2.2-Therapeutic equipments:

2.2. (a) Iontophoretic device:

Fig. (2): The iontophoresis device (Adapted from Ibrahim et al., 2021).

2.2. (b) Botulinum toxin type A:

• Botox Allergan[®](Irvine, CA, USA) will be used .

It is 100 U vacuum-dried powder in a single-use vial for reconstitution diluted in 2 mL of sterile, preservative-free 0.9% saline to constitute a solution at a concentration of 4 U/0.1 mL) (Elhefnawy et al., 2016).

3-Procedures of the study:

3.1-Measurement procedures:

Both sonography and POSAS will be used for assessment of hypertrophic scar pre treatment and post treatment (after 3 months then after 6 months as follow up).

3.1. (a)Sonography

High frequency ultrasound is the most common used technique for scar assessment. Its inferior resolution compared to optical equivalents is mitigated by its superior penetration depth allowing thickness analysis, even in severe scar thickening. The working mechanism is based on refection of sound waves of structures with different acoustic impedances and the analysis of the refection time to determine the depth of the structure. The penetration depth ranges from the upper dermal layers to full-thickness skin and subcutaneous structures, depending on the employed frequency (Téot et al., 2020).

3.1. (b) Patient and Observer scar Assessment Scale (POSAS):

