The scar will be rated numerically on a ten-step scale by both the patient and doctor on six items: vascularity, pigmentation, thickness, relief, pliability, and surface area on the Observer Scale. The Patient Scale consists of pain, itchiness, color, stiffness, thickness, and irregularity of the scar. One of the reasons POSAS was chosen for scar evaluation is because it is the only scar assessment tool to include a component for patients to fill in. Furthermore, its distinctive feature of reflecting subjective symptoms like pain and pruritus and because of its appropriateness for everyday practice (Kant et al., 2018).

Also, The Arabic version of the (POSAS) is an easy-to-administer, simple, reliable and valid tool for assessment of burn scar and for use on Egyptian population. It is advised to be used in clinical practice as well as scientific researches (Nossier et al., 2018).

15

Observer Scar Assessment Scale

normal skin	1	2	3	4	5	6	7	8	٩	10	worst scar imaginable
Vacantariantian		•	3	•	5	0	,	0		10	worst scar imaginable
vascularization	0	0	0	0	0	0	0	0	0	0	
Pigmentation	0	0	0	0	0	0	0	0	0	0	Нуро 🛛
											Mix 🗆
											Hyper 🛛
Thickness	0	0	0	0	0	0	0	0	0	0	
Relief	0	0	0	0	0	0	0	0	0	0	
Pliability	0	0	0	0	0	0	0	0	0	0	
											+
Total score Observer Scar Scale:											
Patient Scar Assessment Sc	cale	2									
No, no complaints	1	~									
		2	3	4	5	6	7	8	9	10	Yes, worst imaginable
Is the scar painful ?	0	2	3	4 0	5 0	6 0	7 0	8 0	9 0	10 0	Yes, worst imaginable
Is the scar painful ? Is the scar itching?	0	2 0 0	3 0	4 0	5 0	6 0	7 0 0	8 0 0	9 0	10 0	Yes, worst imaginable
Is the scar painful ? Is the scar itching?	0	0	3 0	4 0	5 0	6 0	7 0 0	8 0	9 0	10 0	Yes, worst imaginable
Is the scar painful ? Is the scar itching? No, as normal skin	0 0 1	2 0 0 2	3 0 0 3	4 0 0	5 0 5	6 0 6	7 0 0 7	8 0 0 8	9 0 0 9	10 0 0 10	Yes, worst imaginable Yes, very different
Is the scar painful ? Is the scar itching? No, as normal skin Is the color of the scar different?	0 0 1 0	2 0 2 0	3 0 0 3 0	4 0 0 4	5 0 5 0	6 0 0 6	7 0 7 0	8 0 0 8 0	9 0 0 9	10 0 10	Yes, worst imaginable Yes, very different
Is the scar painful ? Is the scar itching? No, as normal skin Is the color of the scar different? Is the scar more stiff ?	0 0 1 0	2 0 2 0 0	3 0 3 0	4 0 4 0	5 0 5 0	6 0 6 0	7 0 7 0	8 0 8 0	9 0 9 0	10 0 10 0 0	Yes, worst imaginable Yes, very different

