In this study, the descriptive statistics (the mean and the standard deviation) will be calculated for all subjects in all groups of the study to determine the homogeneity of the groups.

Analytical statistics:

Comparison will be made by student's t-test to compare the variables between all groups of the study. Paired t-test was used to compare before and after treatment in the same group. A value of $p \le 0.05$ will be considered statistically significant (Maronna et al., 2006).

Sample size:

Sample size calculation is performed using G*POWER statistical software (version 3.1.9.2; Franz Faul, Universitat Kiel, Germany) based on data of VSS from the previous study (Elshahed et al., 2020) who reported a significant effect of botulinum toxin compared with control in treating hypertrophic scars. The required sample size for this study was 38 subjects per group. Calculations were made using α =0.05, power 90% and effect size = 0.76 and allocation ratio N2/N1 =1.

Test family	Statistical test									
t tests 🗸 🗸	Means: Difference between two independent means (two groups)									
Type of power analy	/sis									
A priori: Compute i	required samp	le size – given α,	power, and effect size	~						
Input Parameters			Output Parameters							
	Tail(s)	Two \vee	Noncentrality parameter δ	3.3284740						
Determine =>	Effect size d	0.7636043	Critical t	1.9925435						
	α err prob	0.05	Df	74						
Power (1-β err prob)		0.9	Sample size group 1	38						
Allocation ratio N2/N1		1	Sample size group 2	38						
			Total sample size	76						
			Actual power	0.9074163						

REFERENCES

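### The 90% power belongs to VSS, a scale the trial does not plan to measure, and the supplied text names no primary outcome or visit to carry it

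*Combined protocol and SAP*

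**What the plan says.** The sample-size paragraph appears twice, under 1-Subjects (Sample size) and under 4-Statistical procedures. Both give two-sided α = 0.05 (sidedness from the printed G*Power table), 90% power, effect size 0.76 (0.7636043 in the table) and equal allocation, hence 38 per group. The effect size is "based on data of VSS from the previous study" of botulinum toxin in hypertrophic scars. VSS is not spelled out and appears nowhere else in the supplied text.

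The measurement sections list two instruments:
- **Sonography** (2.1(a)): "A high-resolution B-image sonogram of every patient will be taken before and after treatment".
- **POSAS** (2.1(b)): "It consists of two parts; one for the patient (Patient scale; POSAS Patient) and one for the physician (Observer scale; POSAS Observer".

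Section 3.1 schedules both before treatment and "post treatment (after 3 months then after 6 months as follow up".

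Under Analytical statistics, "Comparison will be made by student's t-test to compare the variables between all groups of the study", and p ≤ 0.05 "will be considered statistically significant". No outcome or visit is singled out. The text does not say whether the groups are compared on post-treatment values or on changes from baseline.

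**The concern.** A power statement is about one comparison: an outcome, a time point and a form of analysis. Here the effect size comes from one scale and the trial measures others. A standardised effect depends on both the difference and the SD of the scale concerned, and the plan gives neither for sonography or POSAS. The trial's only argument for its size therefore rests on an outcome it will not record.

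The second gap makes this worse. With no primary outcome or visit, a significant result on any of the scores at either visit could be presented as the trial's finding, and nothing in the plan says which result counts.

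**Working it through.** **Inputs.** From the plan: d = 0.7636043 (0.76 rounded), α = 0.05 two-sided, n = 38 per group, two independent means. Assumed here: the alternative values of d, the correlations between tests, and one sonographic variable per visit.

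**1. The plan's own figure.** Power comes from the noncentral t distribution with 2n − 2 degrees of freedom and noncentrality d × √(n/2).
- Noncentrality: 0.7636043 × √19 = 3.3285.
- Critical t on 74 df: 1.9925.
- Power: 0.9074.

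All three agree with the printed output. With 37 per group power is 0.8998, so 38 is the smallest n that reaches 90%. The calculation is correct for the d entered.

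**2. Outcomes side by side.**

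| Where | Outcome |
|---|---|
| Sample size (sections 1 and 4) | VSS |
| Measurement tools (Delimitations; 2.1; 3.1) | Sonography, POSAS Patient, POSAS Observer |
| Analysis (section 4) | All variables, unranked |

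No section links the first row to the second.

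**3. Power for a measured outcome.** The plan gives no effect size for these outcomes, so d is varied with n = 38 per group:

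| Assumed true d | Power |
|---|---|
| 0.5 | 0.58 |
| 0.6 | 0.73 |
| 0.7 | 0.85 |
| 0.76 | 0.90 |
| 0.8 | 0.93 |

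Read the other way, 38 per group has 80% power at d = 0.65. It has 90% power at d = 0.753, and 0.905 at d = 0.76.

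**4. Unranked tests.** Three scores (one sonographic variable, POSAS Patient, POSAS Observer) at two post-treatment visits give 3 × 2 = 6 between-group tests. Suppose there is no true effect.
- If the tests are independent, the chance of at least one p ≤ 0.05 in either direction is 1 − 0.95⁶ = 0.265.
- If independent, the chance of at least one in favour of treatment is 1 − 0.975⁶ = 0.141.
- For equally correlated normal test statistics:

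| Assumed correlation | Any false positive | Favouring treatment |
|---|---|---|
| 0 | 26% | 14% |
| 0.5 | 21% | 10% |
| 0.8 | 14% | 7% |

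A single prespecified test would give 5% and 2.5%.

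**The case against.** **Borrowing an effect size is ordinary practice, and the test matches.** This stands in part. The G*Power set-up (two independent means, two-sided, 1:1) is the planned between-group Student's t-test, so the form of the comparison is not in doubt. What is missing is its outcome, its visit, and whether values or changes are compared. If there is a reason to expect 0.76 on POSAS or sonography, the plan could give it in one sentence; it gives none.

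**The trial may still have 90% power.** This is true. A reader might infer that the trial is underpowered. The documents do not support that: power exceeds 90% if the true effect on the chosen outcome is 0.76 or more.

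**26% overstates the false-positive risk.** Accepted. Repeated scores on the same scars will hardly be independent, so 14–21% is the more relevant range, and only about half of it favours treatment. The count of six also assumes a single sonographic variable, which the plan does not define.

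**A non-significant result would be uninterpretable.** A reader might infer this too, since the 95% confidence interval has a half-width of about 0.46 SD and could include both 0 and 0.76. But that half-width follows from 38 per group and α alone. It would be the same if 0.76 had come from POSAS data, so it is not a consequence of this defect.

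**A primary outcome may be named elsewhere.** Possibly. Some front pages were removed and no registry record was available. The finding is limited to the supplied text, which does include the measurement and statistics sections where a primary outcome would be expected.

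**Conclusion.** The point holds, and the plan should be changed. The 90% figure is computed correctly but for VSS, which is not a planned measurement. For each measured outcome it is unshown, not false. Over an assumed range of d from 0.5 to 0.76, power at 38 per group runs from 0.58 to 0.90, and the documents do not say where in or beyond that range sonography or POSAS would fall.

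With no primary outcome or visit named in the supplied text, the plan as written allows at least six unranked tests at 5%. The chance of at least one false positive is about 14–21% at assumed correlations of 0.8–0.5, of which about 7–10% favours treatment. If the tests were independent the figures would be 26% and 14%. These rest on the assumed correlations and on one sonographic variable per visit.

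**What to change.** 1. Before any between-group comparison, name one primary outcome, one visit and one form (post-treatment value or change from baseline). If sonography is chosen, define the variable to be measured. The choice is the investigator's. Label all other between-group comparisons secondary.

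2. Replace the VSS sentence in both places with: *38 per group with complete data detects a standardised difference of about 0.76 with 90% power, or about 0.65 with 80% power, in [named outcome, visit, form] (two-sided 5%).* Then say why a difference of that size is plausible for that outcome, or that no outcome-specific estimate was available.

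**Cost.** No extra patients or visits. The other outcomes become secondary, and the stated power becomes conditional on an effect that may not be reached (0.58 if the true d is 0.5). Step 1 settles which result counts. Step 2 only discloses the effect-size gap: it makes the claim accurate but adds no power, and if no outcome-specific estimate exists, 38 per group remains without an outcome-specific justification.

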The second phase of wound healing is the proliferative phase. This phase of new tissue formation occurs approximately 2–3 days after tissue damage and may last for 3–6 weeks. Active cellular proliferation and migration characterize this phase. Keratinocytes migrate to the damaged dermis; new blood vessels grow inward within the damaged tissue; and new capillaries replace the fibrin matrix with granulation tissue via the actions of macrophages and fibroblasts. Granulation tissue forms a new substrate for keratinocyte migration. Keratinocytes proliferate and mature within granulation tissue along the wound margin, restoring the protective function of the epithelium. In the late proliferative phase, a portion of the

Approved date: 17/5/2022

fibroblasts differentiates into myofibroblasts in association with macrophages. Fibroblasts and myofibroblasts produce extracellular matrix (ECM), mainly in the form of collagen; this accumulated collagen forms most of the eventual scar. Other constituents of ECM include elastin, hyaluronic acids and proteoglycans. Myofibroblasts, which contain actin filaments, have contractile properties and help bring the edges of the wound together over time (Lee and Janget., 2018).

Once wound closure is accomplished, the final remodelling phase commences. This phase is characterized by the degradation of excessive tissue, transforming immature healing products into a mature form. Remodelling may last for a year or more. Excessive ECM is degraded and remodelled from type III collagen, the main component of ECM present during the early wound healing process, to mature type I collagen (Lee and Janget., 2018).

1.2- Hypertrophic scar formation:

An imbalance between the proliferation and degradation of extracellular matrix components leads to excessive scar formation. Risk factors for this include delayed epithelialization, wound infection, specific anatomic locations, or genetic predispositions (Jeschke et al., 2020).

On a molecular level, increased activity regarding scar proliferation is commonly mediated through inflammatory cells that secrete TGF- β 1 and β 2 which induce a fibrogenic response within the scar tissue. At the same time, scar remodeling stimulated through matrix metalloproteases and TGF- β 3 is decreased. Excessive scar formation is dependent on both the severity of the inflammation and the type of the immune response (Jeschke et al., 2020).

2.1: Botulinum toxins:

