Positioning should begin immediately post injury and maintain during the entire process. Positioning should be carried out together with proper ROM training, otherwise, a prolonged fixed position will also result in reduced ROM and contracture. Positioning could be achieved through various modalities including pads, pillows, headboard, foam pads, splints and restraint belts (Cen et al., 2015).

Stretching and early mobilization:

Patients should be encouraged to get out of bed and exercise as soon as they are fit enough to do so. Therapeutic exercise encompasses ambulation of joints, consideration of neurovascular integrity, improving cardiovascular and respiratory capacity, coordination, balance, muscle strength and endurance, exercise performance and functional capacity. Exercise also helps the patient to experience a general feeling of wellbeing and a sense of confidence and achievement (**Procter., 2010**).

Massage therapy:

Massage therapy, manual or mechanical (i.e., compressed air, threadlike showers, vacuotherapy, etc.), is standard therapy in rehabilitation centers specializing in the treatment of scars and burns. Although there is no scientific evidence, it has been shown that massage therapy not only reduces scar-related pain and itching, but also increases range of motion, reveals patients' anxiety and improves their mood and mental status. Mechanical compression is shown to reduce collagen synthesis by several mechanisms. These include decreased blood, oxygen and nutrients delivery to the scar, MMP-28 (matrix metalloprotease-28) downregulation and increase of PGE2 (prostaglandin-E2), which activates collagenase (Arno et al., 2014).

Pressure therapy:

pressure therapy is believed to work by reducing perfusion and oxygen concentrations reaching the scar surface resulting in reduced collagen synthesis. Moreover, pressure on scars reduces hydration, decreases angiogenesis, and induces apoptosis. A variety of materials can be used to provide pressure such as custom-fitted splints and adhesive plaster fittings while the efficacy is mostly dependent on the scar location with limbs and trunks being most appropriate for pressure therapy. Pressure garments can help reduce pain and itching associated with scars (Elsaie., 2021).

4-Statistical procedures:

Descriptive statistics:

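### Scar age and body site vary by design and location is said to matter, but the between-group t-test uses neither factor, which costs precision and leaves any imbalance to post hoc handling

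*Combined protocol and SAP*

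**What the plan says.** Chapter III, 1.2.a (Inclusion Criteria) admits a "Patient with hypertrophic scar (3-6) months after burn healing" and adds that scars may be at different body sites. Outcomes are measured "pre treatment and post treatment (after 3 months then after 6 months as follow up".

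The protocol's own background gives reasons to think that these features matter:

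- Chapter II, 1.1 (Wound healing process), on the remodelling phase: "Remodelling may last for a year or more".
- Chapter II, 1.2 (Hypertrophic scar formation) lists particular anatomic locations among the risk factors for excessive scarring.
- Chapter II, 3.2 (Factors influencing iontophoretic process) says that the effect depends on the tissue under the electrodes, including its thickness, permeability and pores.
- Chapter III, 3.2(c), on pressure therapy, which both groups receive: "efficacy is mostly dependent on the scar location with limbs and trunks being most appropriate for pressure therapy".

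On allocation, Chapter III, 1.1 (Design of the study) says only that "the patients will be randomly assigned into two equal groups (38 patients for each group". It mentions no strata, blocks or minimisation. Section 4 (Statistical procedures) compares groups by Student's t-test without covariates. It uses means and SDs to judge whether the groups are homogeneous, and states no action if they are not.

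**The concern.** The protocol admits patients who differ on two features known or visible before treatment, and gives reasons why at least one of them, site, should relate to outcome. Neither the stated allocation nor the analysis then uses them. Two things are at stake.

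- **Precision.** Outcome variation that these features explain stays in the error term, so the interval is wider than it need be.
- **Discretion.** The plan looks for imbalance but has no rule for responding to it. If the groups differ visibly in scar age or site, any adjustment would be chosen after the data are seen.

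**Working it through.** **1. The plan's own figure.** Section 4 states: "Calculations were made using α =0.05, power 90% and effect size = 0.76 and allocation ratio N2/N1 =1". Its software printout uses d = 0.7636043, two-sided. With n = 38 per group:

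- noncentrality = d × sqrt(n/2) = 0.7636 × sqrt(19) = 3.328
- df = 74, critical t = 1.9925
- power = 0.9074, as printed; at 37 per group it is 0.8998

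So "The required sample size for this study was 38 subjects per group" reproduces, and the sample size is not in question.

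**2. Validity of the unadjusted test.** In simulation, scar age was uniform over 3-6 months and site was binary 50/50. Together they explained R² = 0, 0.10, 0.25 or 0.40 of outcome variance, in equal shares (all assumed). Type I error of the planned t-test was 4.9%, 4.9%, 5.0% and 4.9%. Its power stayed at 0.907.

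**3. Precision given up.** The interval narrows by 1 − sqrt(1 − R²), and the noncentrality becomes 3.328 / sqrt(1 − R²) on 72 df.

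| R² (assumed) | Narrowing | Noncentrality | Power |
|---|---|---|---|
| 0.10 | 1 − 0.949 = 5.1% | 3.509 | 0.933 |
| 0.20 | 1 − 0.894 = 10.6% | 3.721 | 0.956 |

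These figures ignore the small cost of estimating two extra coefficients. That cost inflates the variance by a factor of about 1 + 2/71 = 1.028, or about 1.4% in interval width. Allowing for it, net narrowing is 1 − 0.949 × 1.014 = 3.8% and 1 − 0.894 × 1.014 = 9.3%, and power is about 0.93 and 0.95. If the factors explain nothing, adjusted power is about 0.90 instead of 0.907.

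**4. How large chance imbalance can be.** The number of patients in a category who fall in one arm is hypergeometric (76 patients, 38 drawn).

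- Category held by 38 of 76 (50%, assumed): P(gap ≥ 6/38 = 16 points) = 0.251; P(gap ≥ 8/38 = 21 points) = 0.108.
- Category held by 23 of 76 (30%, assumed): P(gap ≥ 20 points) = 0.045.
- Scar age as a continuous measure, uniform over 3-6 months (assumed): SD = 3/sqrt(12) = 0.87 months. The SE of the arm difference is 0.87 × sqrt(2/38) = 0.87 × 0.229 = 0.20 months, so the 95% range is ±0.39 months. A gap of 0.5 months or more has probability 1.2%.

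**5. What such a gap does to the estimate.** A 50/50 factor whose two levels differ by D (in outcome SDs) explains D²/4 of the variance. Splitting R² equally, each factor has D = 2 × sqrt(R²/2).

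- R² = 0.10: D = 0.447; shift = 0.447 × 8/38 = 0.094 SD (12% of 0.76)
- R² = 0.20: D = 0.632; shift = 0.632 × 8/38 = 0.133 SD (about 18% of 0.76)

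The SE of the treatment difference is sqrt(2/38) = 0.229 SD, so these shifts are 0.4 to 0.6 of one standard error, in either direction.

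**6. Error given an extreme imbalance.** At the 95% limit of imbalance (1.96 × 0.229 = 0.45 SD), type I error of the unadjusted test is 5.9% for a factor correlated 0.2 with outcome and 7.4% for 0.3. These bracket most of the range in step 5, where r = sqrt(R²/2) = 0.22 to 0.32. At a typical, one-SE imbalance it is 4.6%, below nominal.

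**The case against.** The strongest objection is that nothing here is an error. Randomisation leaves chance differences, the t-test's standard error already allows for them, and step 2 confirms it. Entry is also already restricted to a three-month window of scar age and to ages 20-40. The documents give no scar-age distribution, site distribution or prognostic strength, so every figure for benefit rests on assumption. All of this stands, and it limits the point to efficiency and pre-specification.

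Several stronger readings are tempting, and the documents do not support them.

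- **That chance imbalance biases the trial or would pass for a treatment effect.** It is not systematic, and it can hide an effect as easily as mimic one.
- **That a 21-point gap could produce 28% of the planned effect.** This needs a factor whose levels differ by 1.0 SD (0.211 × 1.0 / 0.76). One such factor explains 1.0²/4 = 25% of the variance, already more than the 10-20% assumed here for both factors together.
- **That location governs response to the whole background programme.** The statement concerns pressure therapy, one of four components.
- **That scars 3 and 6 months old have different expected courses.** The remark on remodelling is a general account of wound healing. It makes a difference plausible but does not state one.
- **That the randomisation ignores these factors.** The method is barely described; one can say only that no stratification is stated.

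It is also fair to object that stratified blocks have a price. No sham is described for the control group and no concealment is described, so small blocks within strata could make allocations easier to guess.

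**Conclusion.** The point holds as a matter of efficiency and pre-specification. The planned comparison is valid on average, but it discards two baseline features, one of which the protocol itself says matters, and it gives no rule for an observed imbalance. If the two features explain 10-20% of outcome variance, the loss is about 5-11% of interval width (about 4-9% net of the cost of estimation), and power of 0.907 where about 0.93-0.96 was available from the same 76 patients. If they explain nothing, adjustment costs under one percentage point of power. Because the proposed model also contains the baseline outcome, the 10-20% should be read as variance explained beyond baseline. The power figures take the plan's design effect of 0.76 SD at face value, and the plan's assumption that "All subjects will continue in the study". The change is cheap and worth making. It does not alter the sample size.

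**What to change.** In section 4, replace the between-group t-test with a pre-specified linear model (ANCOVA) at each post-treatment visit. Include treatment group, baseline value of the outcome, scar age since healing (continuous, in months), and site grouped as limb or trunk versus other. State that this analysis is used whatever the observed balance, and record site at baseline.

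The cost is two degrees of freedom for scar age and site, one for the baseline value, and one more baseline field. Scar age is already needed to apply the entry criterion. Site is evident when the scar is assessed, but the documents do not describe recording it.

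Optionally, if recruitment has not started, stratify allocation by scar age (3 to <4.5 versus 4.5-6 months) and grouped site, using concealed lists with randomly varying block sizes. The arms may then differ slightly from 38/38, and allocations may be more predictable in an apparently unblinded trial. If recruitment has begun, covariate adjustment alone gives most of the benefit, provided that it is fixed before outcome data are examined.
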